10.2 Handling of Multiplicity

No adjustment for multiple comparisons is used.

10.3 Primary Efficacy Analysis

The primary efficacy variable is SVR₁₂ (HCV RNA < LLOQ 12 weeks after the last actual dose of study drug).

The primary efficacy endpoint is:

- Non-inferiority of the ABT-493/ABT-530 8-week regimen (Arm A) to the SOF and RBV 12 week regimen (Arm B) in SVR₁₂ using a non-inferiority margin of 10% in the ITT population.

For the primary efficacy endpoint, to show non-inferiority of the SVR₁₂ rate of the ABT-493/ABT-530 8-week regimen (Arm A) to that of the SOF and RBV 12-week regimen (Arm B), the percentage of subjects achieving SVR₁₂ will be calculated for each arm and a two-sided 95% confidence interval for the difference in SVR₁₂ rates (Arm A minus Arm B) will be calculated using the normal approximation to the binomial distribution, unless the SVR₁₂ rates are 100% for both Arm A and Arm B, then the Wilson's score method will be used for the confidence interval instead. All subjects in the ITT population will be used when calculating SVR₁₂. If the lower bound of the confidence interval for the difference is above the non-inferiority margin of -10%, then the ABT-493/ABT-530 8-week regimen will be considered non-inferior to SOF and RBV 12 week regimen.

10.4 Interim Analysis

The efficacy variable for the interim analysis is SVR₄ (HCV RNA < LLOQ 4 weeks after the last actual dose of study drug).

The interim efficacy endpoint analysis is:

- The difference between the ABT-493/ABT-530 8-week regimen (Arm A) to the SOF and RBV 12 week regimen (Arm B) in SVR₄.

For the interim analysis, the difference between the SVR₄ rate of Arm A and that of the Arm B will be calculated along with a two-sided 95% confidence interval for the difference in SVR₄ rates (Arm A minus Arm B) using the normal approximation to the binomial distribution, unless the SVR₄ rates are 100% for both Arm A and Arm B, then the Wilson's score method will be used for the confidence interval instead. All subjects in the ITT population will be used when calculating SVR₄ rates.

10.5 Secondary Efficacy Analyses

The following secondary endpoints will be summarized:

- the percentage of subjects achieving SVR₁₂ for Arm A (the ABT-493/ABT-530 8-week regimen)
- the percentage of subjects in each treatment arm with on-treatment virologic failure (defined as confirmed increase of > 1 log₁₀ IU/mL above nadir during treatment, confirmed HCV RNA ≥ 100 IU/mL after HCV RNA < LLOQ during treatment, or HCV RNA ≥ LLOQ at the end of treatment with at least 6 weeks of treatment), and
- the percentage of subjects in each treatment arm with post-treatment relapse (defined as confirmed HCV RNA ≥ LLOQ between end of treatment and 12 weeks after the last dose of study drug among subjects who completed treatment as planned with HCV RNA < LLOQ at the end of treatment, excluding subjects who have been shown to be reinfected).

For the first secondary efficacy endpoint, the percentage of achieving SVR₁₂ in Arm A and a two-sided 95% confidence interval will be calculated using the normal approximation to the binomial distribution, unless the rate is 100% and then the Wilson's score method will be used.

The percentage of subjects with on-treatment virologic failure and post-treatment relapse will be summarized for each treatment arm. Two-sided 95% confidence intervals will be provided for rates within treatment arms and for the difference between arms (Arm A minus Arm B) using Wilson's score confidence intervals. For the analysis of relapse and reinfection, completion of treatment is defined as any subject assigned to the 12-week treatment with study drug duration of 77 days or greater; or any subject assigned to the 8-week treatment with study drug duration of 52 days or greater. Subjects with probable reinfection based on HCV sequencing or differing post-treatment HCV genotype or subtype will be summarized separately from relapse.

In addition, a summary of reason for SVR₁₂ non-response (e.g., on-treatment virologic failure, relapse, re-infection, other) will be provided for each treatment arm.

Similar secondary endpoint analyses (SVR₄ in Arm A, on-treatment virologic failure in each arm, and relapse through PT Week 4) will be performed for the interim analysis.

10.6 Sensitivity Analyses for SVR

The following analysis approaches will be used as sensitivity analyses for evaluating SVR₁₂ rates within and between treatment arms for the primary efficacy endpoint:

- A two-sided 95% confidence interval for the SVR₁₂ rates within each arm will be calculated using a Wilson score interval.
- The percentage of subjects achieving SVR₁₂ will be compared using a logistic regression model with treatment arm as a factor, and baseline log₁₀ HCV RNA level, HCV genotype 2 subtype, and prior HCV treatment history as covariates.

- The difference in SVR₁₂ rates (Arm A minus Arm B) will be analyzed using a stratum-adjusted Mantel-Haenszel (MH) proportion with a continuity correction for variance, adjusting for both of the randomization stratum (described in Section 5.2).
- A two-sided 95% confidence interval for the difference in SVR₁₂ rates (Arm A minus Arm B) will be calculated using a Wilson score interval.

The above analyses will be performed on the ITT, and mITT-GT-VF populations, as applicable. The same sensitivity analyses will be performed for SVR₄ in the interim analysis.

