4.2 Design Diagram

This is a Phase 3, randomized, open-label, active-control, multicenter study to evaluate the efficacy, safety and pharmacokinetics of ABT-493/ABT-530 in chronic HCV GT2-infected HCV DAA treatment-naïve Japanese adult subjects without cirrhosis. This study consists of a Treatment Period (TP) and a Post-Treatment (PT) Period.

Figure 1. Study Schematic

Approximately 120 HCV GT2-infected DAA treatment-naïve subjects (including subjects who are IFN treatment experienced with or without RBV) without cirrhosis will be enrolled into one of two treatment arms (80 subjects into Arm A and 40 subjects into Arm B)

- Arm A: ABT-493/ABT-530 300 mg/120 mg QD for 8 weeks;
- Arm B: SOF 400 mg QD plus RBV (600 – 1000 mg based on weight divided BID) for 12 weeks.

Subjects meeting all eligibility criteria will be randomized to Arms A or B. The randomization will be stratified by prior IFN-experience (naïve versus experienced) and screening HCV RNA viral load (< or ≥ 6 million IU/mL). Subjects will be randomized in a 2:1 ratio to Arms A (80 subjects) or B (40 subjects).

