4.3 Sample Size

It is planned to enroll a total of 120 subjects in this study. The primary efficacy endpoint of SVR₁₂ will be assessed between treatment Arms A and B.

For the primary endpoint, with 80 subjects in the ABT-493/ABT-530 8-week arm (Arm A) and 40 subjects in the SOF plus RBV 12 week arm (Arm B) and assuming that 96% of the subjects in Arm A achieve SVR₁₂ and 95% of subjects in Arm B (Table 1) achieve SVR₁₂, this study has > 80% power to demonstrate non-inferiority of the ABT-493/ABT-530 8-week treatment arm compared to the active control in SVR₁₂ rate (i.e., a two-sided 95% lower confidence bound for the difference above the non-inferiority margin of –10%). The 10% margin is considered to be an appropriate potential loss of efficacy given the possibility that the current regimen may provide additional clinical advantage over the comparator regimen by shortening the duration of treatment to 8 weeks and eliminating the need for RBV.

Table 1. SVR₁₂ Rates in GT2-Infected Non-Cirrhotic Subjects

| Trial | SVR (n/N) | SVR (%) |
|-----------------------------|------------------|------------------------|
| FISSION ¹ | 59/61 | 97% |
| POSITRON ¹ | 85/92 | 92% |
| FUSION ¹ | 26/29 | 90% |
| VALENCE ¹ | 59/63 | 94% |
| Japanese Study ² | 132/136 | 97% |
| Total | 361/381 | 95%^a |

a. The SVR rate is an unweighted average across the studies.

Note: Data included in the table is for 12-week SOF plus RBV regimen across multiple clinical trials in GT2-infected non-cirrhotic subjects.

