Subgroup analysis will also be performed on relevant combinations of subgroup variables if deemed clinically meaningful.

For the subgroup analyses, the presence of baseline resistance-associated variants as listed above are defined in Section 10.9.1.

All subgroup analyses will be performed for SVR₄ in the interim analysis except

- Presence of baseline resistance-associated variants (any NS3 variant [yes/no]; any NS5A variant [yes/no]; any NS3 and any NS5A [yes/no], any NS3 or any NS5A [yes/no]) and (NS3 only, NS5A only, both NS3 and NS5A, or none).

A logistic regression model will be used to explore the associations between each of the subgroup variables and SVR₁₂ by fitting a logistic regression model on all subjects in the mITT-GT-VF population. Among all candidate predictors, continuous measurements will be used where possible (e.g., continuous baseline log₁₀ HCV RNA level) in the logistic regression model. For the variables on presence of baseline resistance-associated variants, only one unique variable (NS3 only vs. NS5A only vs. both NS3 and NS5A vs. none) will be used in the logistic regression model. A stepwise logistic regression approach will be used to assess the strength of each subgroup variable in predicting SVR₁₂, with a significance level of 0.10 to enter and remain in the model.

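### The logistic sensitivity model in SAP 10.6 rests on about five expected failures, has no sparse-data method, and as specified gives no risk difference to set beside the primary analysis

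*SAP*

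**What the plan says.** Section 4.3 plans 80 subjects in Arm A and 40 in Arm B, "assuming that 96% of the subjects in Arm A achieve" SVR₁₂ and "95% of subjects in Arm B (Table 1) achieve" it. Section 10.3 defines the primary endpoint as non-inferiority of Arm A to Arm B, "using a non-inferiority margin of 10% in the ITT population", judged by the lower limit of a 95% interval for the difference in rates.

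Section 10.6 gives four sensitivity approaches for that endpoint. One is the logistic model: "The percentage of subjects achieving SVR₁₂ will be compared using a logistic regression model with treatment arm as a factor", with baseline log₁₀ HCV RNA, genotype 2 subtype and prior treatment history as covariates. The others are Wilson intervals within arms, a stratum-adjusted Mantel-Haenszel difference with a continuity-corrected variance, and a Wilson interval for the difference. All are to be run in ITT and mITT-GT-VF where applicable, and repeated for SVR₄ at the interim analysis. The SAP does not say which quantity the logistic model reports, or what happens if it cannot be fitted.

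Section 10.7 adds a second logistic analysis, in mITT-GT-VF, over the subgroup variables: "A stepwise logistic regression approach will be used to assess the strength of each subgroup variable in predicting SVR₁₂", with 0.10 as the level to enter and to stay.

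**The concern.** A logistic model needs failures in each group that it compares. If one arm has none, the likelihood keeps rising as the arm coefficient moves toward infinity. Ordinary maximum likelihood then returns no finite estimate, and the Wald interval and test that software prints have no meaning. The same happens to a covariate's coefficient if all failures fall on one side of it.

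The SAP provides for sparse data elsewhere: a Wilson fallback when both arms are at 100% (10.3), the continuity correction for Mantel-Haenszel (10.6.2), Zelen's exact test and a 10-subject minimum for subgroup intervals (10.7), and Fisher's exact test for baseline variants (10.9). The two logistic models have no such provision, so the remedy would have to be chosen after the data are seen.

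There is also a question of scale. The usual result of such a model is an odds ratio tested against 1. A non-significant odds ratio does not support non-inferiority, and the SAP gives neither an odds-ratio margin nor a conversion to a risk difference.

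**Working it through.** **Inputs.** Arm sizes 80 and 40, SVR₁₂ rates 96% and 95% (section 4.3); margin −10 points on the risk difference (4.3, 10.3); four slopes in the 10.6 model if subtype has two levels (arm, log₁₀ RNA, subtype, prior treatment). With these inputs, exact enumeration of the normal-approximation interval rule gives 87.6% power. The stated power above 80% is therefore reproduced and is not in dispute.

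**Expected failures.** 80 × 0.04 + 40 × 0.05 = 3.2 + 2.0 = 5.2, or 5.2 / 4 = 1.3 per slope. The probability of four or fewer failures in total is 40%, and of nine or fewer 96%. By its definition in 5.1.2, mITT-GT-VF only removes subjects from ITT, including every non-virologic failure, so it can have no more failures than ITT.

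**Probability that an arm has no failures.** P = 1 − (1 − p_A^80)(1 − p_B^40).

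| SVR₁₂ A/B | Expected failures | p_A^80 | p_B^40 | P(no failures in at least one arm) |
|---|---|---|---|---|
| 96%/95% (SAP) | 5.2 | 3.8% | 12.9% | 16.2% |
| 97%/97% (assumed) | 3.6 | 8.7% | 29.6% | 35.7% |
| 98%/97% (assumed) | 2.8 | 19.9% | 29.6% | 43.6% |

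**Separation of the full model.** This needs covariate prevalences that the SAP does not give. Assumed: minor subtype 20–50%, IFN-experienced 15–50%, log₁₀ RNA with SD 0.8, no covariate related to outcome. Trials were simulated at each setting, and separation was detected by linear programming, first for any coefficient and then for the arm coefficient.

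- At 96%/95%, any separation occurred in 30% of trials (both prevalences 50%) to 64% (subtype 20%, experienced 15%).
- At 96%/95%, the arm coefficient itself was non-finite in about 15–17%, in line with the 16.2% above. The corresponding ranges were about 33–37% at 97%/97% and 43–47% at 98%/97%.

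Taking 16% for the arm, the share of separated trials in which the arm estimate stays finite is (30 − 16)/30 = 47% at the low end and (64 − 16)/64 = 75% at the high end.

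**Scale.** The odds ratio equivalent to −10 points at control rate p is [(p − 0.10)/(1.10 − p)] / [p/(1 − p)]. It is 0.44 at p = 90%, 0.30 at 95%, 0.21 at 97% and 0.08 at 99%. No single odds ratio stands for the margin.

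**Stepwise model in 10.7.** The section lists 25 subgroup items. If they were 25 independent null candidates, at least one would pass 0.10 with probability 1 − 0.9^25 = 93%. This only illustrates the scale, because the candidates overlap (creatinine clearance with eGFR; fibrosis stage with the two categories derived partly from it) and tests on so few failures are discrete.

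**The case against.** The strongest reply is that separation does not mean loss of the treatment comparison. If no experienced subject fails, the coefficient for prior treatment diverges but the arm effect is still estimated from the other subjects. That is right. A reader might take the 30–64% range to mean that the treatment comparison fails that often; the calculation does not support this, and 16% is the figure at the planning rates.

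A reader might also infer that the SAP intends to hold an odds ratio against −10%. It does not say so. Nor does it name maximum likelihood, a Wald test or an odds ratio; these are the ordinary reading of an unqualified logistic regression. What stands is narrower: a model listed in support of a risk-difference endpoint has no stated output on that scale.

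Thirdly, the margin is already examined on the right scale in the same section, by the Mantel-Haenszel difference, which adjusts for IFN experience and screening viral load, and by the Wilson difference. Section 10.6.1 adds two imputation analyses with intervals for the difference. All of this stands, and it limits the consequence of the point.

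On 10.7, the SAP presents the model as exploring associations, and nothing is decided from it. To say that it will mostly select noise presumes that every candidate is null, which the document cannot show. Replacing it with separate one-variable estimates leaves the multiplicity: with 25 independent tests at 0.05, at least one would pass with probability 1 − 0.95^25 = 72%.

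**Conclusion.** The point holds for the model in 10.6, as a defect in a supportive analysis. Applied as an ordinary logistic fit, it would give no finite arm estimate in 16% of trials at the SAP's own rates, and in about 36–44% if response is somewhat higher than planned (97%/97% or 98%/97%, assumed). The first figure needs no input from outside the SAP. The 30–64% for separation on any term rests on assumed prevalences and measures whether the whole model fits, not whether the arms can be compared. Where the model does fit, its output cannot be read against the margin as specified.

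A reader might conclude that the non-inferiority claim is in danger. It is not: the primary interval does not use this model, and two other analyses in 10.6 check the margin directly. For 10.7, the supportable statement is that stepwise selection over about 25 overlapping candidates with about five or fewer failures is unreliable.

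**What to change.** In 10.6, fit the same arm and covariate terms by Firth-penalised logistic regression, and report the standardised risk difference (Arm A minus Arm B, averaged over the covariates of all subjects in the population analysed) with a 95% interval that can be read beside the −10% margin. State the interval method in advance, and apply the same specification to mITT-GT-VF and to SVR₄ at the interim.

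The cost is a change of SAP wording and a little more programming; penalised fitting is in standard software. The downside is some shrinkage: the penalty pulls predicted failure rates toward one half, so the text should also say whether the intercept is re-estimated so that the average predicted rate matches the observed one.

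As a secondary suggestion for 10.7, replace stepwise selection with one-variable-at-a-time exact or Firth odds ratios with intervals, without selection by significance, and note that multiplicity remains. The cost is that there would be no multivariable predictor model, which about five failures could not support in any case.

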10.6.1 Imputation Approaches

In addition to imputing SVR₁₂ as described in Section 6.3, SVR₁₂ rates will be calculated using the following other methods to impute missing HCV RNA values:

- imputing any missing HCV RNA values in the SVR₁₂ window by carrying forward the last non-missing (post-baseline) HCV RNA value prior to the SVR₁₂ window;
- impute as described in Section 6.3 but treat SVR₁₂ non-responders who were categorized as "prematurely discontinued study drug with no on-treatment virologic failure" or "missing follow-up data in the SVR₁₂ window" as successes.

For each of these, the percentage of subjects with SVR₁₂ in each arm and the difference between arms will be presented along with two-sided 95% confidence intervals. The same sensitivity analyses will be performed for SVR₄ in the interim analysis.

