6.3 Missing Data Imputation

Missing Data Imputation for SVR

HCV RNA values will be selected for analysis based on the analysis windows defined in Section 6.2. HCV RNA values from central laboratory will be used as described in Section 10.1, unless otherwise specified.

For analyses of SVR, subjects missing a visit HCV RNA value will have backward imputation applied, if possible. For backward imputation, if the nearest HCV RNA value after the SVR window is unquantifiable or undetectable, then it will be used to impute the HCV RNA value in the SVR window. If a subject continues to be missing an HCV RNA value within the appropriate SVR window after performing backward imputation, then this value will be imputed using an HCV RNA value from a local laboratory if available; otherwise, the HCV RNA value for that window will be considered missing. Subjects with missing HCV RNA data in the analysis window, after applying these imputations, will be imputed as a failure of viral response.

Regardless of the imputation method described above, if a subject starts another treatment for HCV, then all HCV RNA values for this subject measured on or after the start date of the new HCV treatment will be excluded from analyses. The subject will be considered a failure for summaries of viral response at all time points after the start of the new HCV treatment.

Missing Data Imputation for Virologic Failure

If HCV RNA values from the central laboratory are missing but a local laboratory value is available in the appropriate time period, then the local laboratory data will be used to assess post-treatment relapse and on-treatment virologic failure.

Missing Data Imputation for PRO Questionnaires

For EQ-5D-3L index and VAS scores, no imputation will be performed for missing items. The missing items of the FSS questionnaire will be imputed with the average score of the answered items as long as more than 50% of the items on the FSS are answered.

If a subject starts another treatment for HCV, then all PRO values for this subject measured on or after the start date of the new HCV treatment will be excluded from analyses.

No imputation will be performed for missing data in other than specified above.

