SVR₄ = HCV RNA $<$ LLOQ in the SVR₄ window (4 weeks after the last actual dose of study drug) without any confirmed quantifiable (\geq LLOQ) post-treatment value before or during that SVR window.

SVR₁₂ = HCV RNA $<$ LLOQ in the SVR₁₂ window (12 weeks after the last actual dose of study drug) without any confirmed quantifiable (\geq LLOQ) post-treatment value before or during that SVR window.

SVR₂₄ = HCV RNA $<$ LLOQ in the SVR₂₄ window (24 weeks after the last actual dose of study drug) without any confirmed quantifiable (\geq LLOQ) post-treatment value before or during that SVR window.

Relapse₄ = confirmed HCV RNA \geq LLOQ between end of treatment and 4 weeks after last actual dose of study drug (up to and including the SVR₄ assessment time point) for a subject with HCV RNA $<$ LLOQ at Final Treatment Visit who completed treatment (defined as study drug duration \geq 52 days for Arm A and \geq 77 days for Arm B), excluding reinfection as described below.

Relapse₁₂ = confirmed HCV RNA \geq LLOQ between end of treatment and 12 weeks after last actual dose of study drug (up to and including the SVR₁₂ assessment time point) for a

subject with HCV RNA < LLOQ at Final Treatment Visit who completed treatment (defined as study drug duration ≥ 52 days for Arm A and ≥ 77 days for Arm B), excluding reinfection as described below.

Relapse₂₄ = confirmed HCV RNA \geq LLOQ within the SVR₂₄ window for a subject who achieved SVR₁₂ and has HCV RNA data available in the SVR₂₄ window, excluding reinfection.

Relapse_{overall} = confirmed HCV RNA \geq LLOQ between end of treatment and up to and including the last HCV RNA measurement collected in the PT Period for a subject with HCV RNA < LLOQ at Final Treatment Visit who completed treatment (defined as study drug duration ≥ 52 days for Arm A and ≥ 77 days for Arm B), excluding reinfection.

Only subjects who have at least one post-treatment HCV RNA value will be included in analyses of relapse. For the analysis of relapse, completion of treatment is defined as any subject with study drug duration of 52 days or greater for Arm A and 77 days or greater for Arm B. If the last available post-treatment value is \geq LLOQ, then the subject will be considered a relapse (i.e., will not require confirmation).

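### The two missing-data sensitivity analyses for SVR can score a subject as a success with no off-treatment sample, or despite a quantifiable one, and no analysis handles missing data less favourably in Arm A than in Arm B

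*SAP*

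**What the plan says.** **Endpoint.** SAP Section 10.1 defines SVR12 as HCV RNA below LLOQ in a window placed "12 weeks after the last actual dose of study drug", with no confirmed quantifiable post-treatment value before or during that window. Table 3 opens the SVR12 window at Study Drug End Day 57 and the SVR4 window at Study Drug End Day 3. Post-treatment data must have Study Drug End Day > 2.

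**Primary rule.** Under Section 6.3, a value still missing after backward and local-laboratory imputation "will be imputed as a failure of viral response". This applies to both arms.

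**Sensitivity methods.** Section 10.6.1 lists two, and repeats them for SVR4 at the interim analysis:

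- The first fills the gap by "carrying forward the last non-missing (post-baseline) HCV RNA value prior to the" SVR12 window.
- The second says to "impute as described in Section 6.3 but treat" two classes of non-responder as successes: those who stopped study drug early without on-treatment virologic failure, and those with no follow-up data in the window.

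**Related text.** Section 10.1 limits Relapse12 to subjects with at least 52 days (Arm A) or 77 days (Arm B) of study drug. Section 10.6 also runs its analyses on mITT-GT-VF, which removes subjects who missed SVR12 for non-virologic reasons.

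**The concern.** SVR12 asks whether the virus stays away once the drug is withdrawn. A value taken on treatment cannot answer that, yet the carry-forward rule accepts one. Section 10.1 applies the stricter principle elsewhere, admitting to the relapse analyses only subjects with at least one post-treatment value.

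The second method has a separate fault: its early-discontinuation class is not confined to missing data, so an observed failure can be turned into a success.

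The set as a whole also leaves a gap. For a non-inferiority claim, the threatening pattern is that missing Arm A subjects are failures while missing Arm B subjects are successes. Nothing listed examines it. A report could then describe the result as robust to missing data without having tested that direction. With 40 subjects in Arm B, one subject is 1/40 = 2.5 points, a quarter of the 10-point margin.

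**Working it through.** **Inputs from the SAP.** Section 4.3: 80 v 40 subjects, "assuming that 96% of the subjects in Arm A achieve" SVR12 and "95% of subjects in Arm B". Section 10.3: margin 10 points, with a two-sided 95% normal-approximation interval for A minus B (Wilson only if both arms are 100%). The SAP gives no dropout or virologic-failure counts, so those below are assumptions.

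**The plan's own figure.** Section 4.3 states that "this study has > 80% power to demonstrate non-inferiority". Enumerating all binomial outcomes under the Section 10.3 rule gives 87.6%, which agrees. The simple unpooled formula gives less: SE = sqrt(0.96×0.04/80 + 0.95×0.05/40) = 0.0408, and Φ(0.11/0.0408 - 1.96) = 76.8%. The stated power is thus reproducible with the plan's own interval, which is used below.

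**Step 1: which values can be carried.**
- SVR12: the window opens on Study Drug End Day 57. A subject with no sample after Study Drug End Day 2 has only an on-treatment or end-of-treatment value to carry. If it is below LLOQ, the subject scores as SVR12.
- SVR4: the window opens on Study Drug End Day 3. Every earlier value is on treatment or within 2 days of the last dose, so nothing else can be carried.

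**Step 2: who the second method re-counts.** Take a subject who stops before day 52 (Arm A) or day 77 (Arm B), has no on-treatment failure, and is later quantifiable. Relapse12 does not apply because treatment was not completed. The subject falls into the early-discontinuation class of the SVR12 non-response reasons and is re-counted as a success. Section 10.8 plans a separate summary of early stoppers who relapse, so the SAP foresees such subjects.

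**Step 3: direction under equal dropout shares.** Let 2k subjects in Arm A and k in Arm B be re-counted. Each rate rises by k/40, so the difference is unchanged. Each p(1-p) falls when p is at least 0.5, so the standard error shrinks and the lower bound rises. Enumeration over k = 1 to 6 with rates of at least 50% showed a rise in every configuration, and no pass became a fail. Carry-forward does the same when last values are suppressed alike in both arms.

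**Step 4: size.** Lower bound = d - 1.96 × sqrt[pA(1-pA)/80 + pB(1-pB)/40], in percentage points, assuming 3 virologic failures in A and 2 in B. For mITT-GT-VF the denominators shrink, and the same formula is used for comparability. Worst case means missing fails in A and succeeds in B.

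| Dropout per arm (A, B) | Primary | All success | mITT-GT-VF | Worst case |
|---|---|---|---|---|
| 2.5% (2, 1) | 75/80 v 37/40: -8.48 | 77/80 v 38/40: -6.68 | 75/78 v 37/39: -6.85 | 75/80 v 38/40: -9.84 |
| 5% (4, 2) | 73/80 v 36/40: -9.92 | 77/80 v 38/40: -6.68 | 73/76 v 36/38: -7.03 | 73/80 v 38/40: -12.91 |
| 10% (8, 4) | 69/80 v 34/40: -12.14 | 77/80 v 38/40: -6.68 | 69/72 v 34/36: -7.40 | 69/80 v 38/40: -18.88 |

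The 5% worst case in full: d = 91.25 - 95.00 = -3.75; SE = 4.675; -3.75 - 1.96 × 4.675 = -12.91.

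**Step 5: when the planned methods can lower the bound.**
- Carry-forward, equal dropout, different last values: 1 virologic failure per arm, 4 missing in A (all last values quantifiable) and 2 in B (both suppressed). Primary 75/80 v 37/40 = -8.48; carry-forward 75/80 v 39/40 = -10.93.
- Second method, more missing in B: 5 and 1 virologic failures, 1 and 3 missing. Primary 74/80 v 36/40 = -8.44; all success 75/80 v 39/40 = -10.93.

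**The case against.** The strongest reply has four parts.

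- **The planned set is not toothless.** A reader might infer that both methods only turn missing into success and that neither can overturn non-inferiority. The SAP does not support that. Carry-forward keeps a quantifiable last value as a failure, and Step 5 shows each method turning a pass into a fail. The second method also probes the case where missing equals failure flatters Arm A, namely more dropout in the 12-week arm. This stands, and it limits the one-direction statement to equal dropout shares and, for carry-forward, to last values suppressed alike.
- **Few subjects may be affected.** An on-treatment value is carried into SVR12 only if there is no sample from Study Drug End Day 3 to 56 and none in the SVR12 window. The definition still excludes anyone with a confirmed quantifiable post-treatment value. This stands for SVR12. It does not help for SVR4, where no post-treatment value can be carried.
- **The worst case is an extreme bound.** Its omission is not a contradiction, and planned summaries and listings of non-response reasons would let a reader work it out. This is fair, and is why the table is proposed as supportive only.
- **The counts are assumed.** At 2.5% dropout the worst case passes, and at 10% the primary already fails. This also stands: the gap matters in between.

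**Conclusion.** The concern holds in a limited form. Two rules in Section 10.6.1 are unsound as written: carry-forward admits on-treatment values into an off-treatment endpoint, and for SVR4 can use nothing later than two days after the last dose; the second method can re-count an observed post-treatment failure as a success. Separately, no listed analysis, mITT-GT-VF included, treats missing data less favourably in Arm A than in Arm B.

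Under the assumed 3 v 2 virologic failures and equal dropout, the consequence appears at about 5% dropout: the primary passes narrowly, the planned alternatives look comfortable, and the opposite-direction bound falls 2.91 points beyond the margin. At 2.5% no conclusion changes.

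A reader might go further and doubt the primary result. The SAP gives no ground for that: non-inferiority rests only on the Section 10.3 ITT interval with missing as failure, and Section 10.6.1 is supportive. The change should be made, but it is not critical.

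**What to change.** 1. In Section 10.6.1, limit carry-forward to values with Study Drug End Day > 2. Subjects without such a value stay failures. Drop carry-forward for SVR4, where nothing eligible would remain.
2. In the second method, keep as a failure any subject with an observed quantifiable post-treatment value, and re-count only those whose outcome is truly unobserved.
3. Add one supportive tipping-point table for the ITT difference in SVR12. Vary the number of missing subjects counted as successes in each arm, and include the corner where Arm A missing fails and Arm B missing succeeds.

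The cost is a few lines of SAP wording and one table from data already collected. The primary analysis and sample size do not change. The downside is that the sensitivity results may look less favourable.
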